14. INFORMATION OF THE PERSON WHO INTENDS TO CONDUCT THE CLINICAL TRIAL⁶¹	
14.1 Sponsor	61
14.2 Principal Investigator.....	61
14.3 Contract Research Organization.....	61
15. OTHER MATTERS NECESSARY TO SAFELY AND SCIENTIFICALLY CONDUCT CLINICAL TRIALS	61
15.1 Clinical Trials Site	61
15.2 Principal Investigator and Clinical Site Staffs	62
15.3 Protocol Violation	62
15.4 Criteria for Treatment of Subjects after Clinical Trials	62
16. REFERENCES	62

CoV2-001: CLINICAL PROTOCOL SYNOPSIS

Study Title: Multicenter, randomized, combined Phase I dose-escalation and Phase IIa double-blind, placebo-controlled study of the safety, tolerability, and immunogenicity of GLS-5310 DNA vaccine administered intradermally against SARS-CoV-2
Number of study sites and Countries/Regions: 5, Korea
Number of study participants: 45 (Phase I), 120 (Phase IIa)
Study Phase: I / IIa
Study Type: Phase I: Dose-ranging Phase IIa: Multi-center, Randomized, Double-blind, Placebo
Study Period: About 20 months from the date of approval of the clinical study by the Ministry of Food and Drug Safety and the Institutional Review Board - Recruitment period for test subjects: about 5 months - Clinical trial period for each subject: at least 48 weeks
Research Hypothesis: GLS-5310 DNA vaccine delivered intradermally (ID) with JM-11 will be safe, well-tolerated and that vaccination will elicit immune responses against SARS-CoV-2 vaccine antigens.
Primary study objectives– Phase I & IIa: 
• Evaluate the safety and tolerability of GLS-5310 vaccine• Determine post-vaccination binding antibody responses induced by GLS-5310 relative to treatment arm
Secondary study objectives– Phase I & IIa: 
• Determine the T cell responses induced by GLS-5310• Determine the neutralizing antibody response induced by GLS-5310
Exploratory study objectives: Phase I exploratory objectives 
• Determine IgG antibody responses after a single dose of vaccine related to treatment arm• Determine whether passive transfer of human serum can protect against pulmonary infection from SARS-CoV-2 challenge in an animal infection model Phase II exploratory objectives 
• Determine the persistence of immune responses following vaccination with GLS-5310• Determine the extent of immune boosting for participants who are seropositive at baseline following vaccination with GLS-5310

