For the Phase I study, the sample size of 15 participants per group will allow detection of an increase in adverse events of 13% with 88% statistical power using a 2-sided alpha of 0.10. The sample size will allow assessment of a difference of 35% in seroconversion between groups after a complete vaccination series or after a single vaccination at a similar statistical power. The sample size will also allow assessment of a difference in geometric mean titers by ELISA, determined by analysis of variance, between dose levels (low dose versus high dose) of 35% with 86% statistical power at an alpha of 0.10. These results will be used to guide selection of vaccination regimen for Phase IIa.

For the Phase IIa study, the sample size of 300 participants, randomized 2:1 vaccine to placebo will allow detection of a difference in adverse events of 18% with 82% statistical power at alpha of 0.05. The sample size will allow assessment of a difference in seroconversion between groups of at least 10% with greater than 95% statistical power at alpha of 0.05. For a sample size of 126 participants, randomized 2:1 vaccine to placebo will yield 80% probability to detect a difference in the rate of adverse events of 28% or greater. A sample size of N=126 will allow detection of a difference in seroconversion of 14% with 80% statistical power. Safety and immunogenicity will be determined at planned Interim Analysis and after all vaccinations are completed.

Safety assessments:

Participants will be monitored at each study visit for adverse events. Laboratory safety assessments will be performed as indicated in the schedule of events to determine whether there are any changes in hematologic parameters, electrolytes, or renal function relative to pre-vaccination assessment. Subjects administered GLS-5310 will be followed for a year from their first vaccination with GLS-5310 regardless of initial study arm randomization. In the Phase IIa study, subjects, will be followed for 48 weeks from first vaccination, however, subjects assigned to placebo and who chose to be vaccinated with GLS-5310, will be followed for a year from first vaccination with GLS-5310 or a total of 60 weeks.

Immunogenicity analysis:

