11.6 Sample Size and Randomization

This clinical trial is a phase 1/2a clinical trial to evaluate the safety and immunogenicity of GLS-5310 for the purpose of preventing COVID-19 set the required number of subjects.

For the phase 1 study, 45 subjects who meet the inclusion and exclusion criteria will be enrolled in order to secure 15 subjects to be vaccinated for investigational drugs for each vaccination group. For the phase 2a study, it was planned to secure 120 subjects based on randomization.

Randomization was performed 1:1 in groups 1b and 1c of the phase 1 study according to the pre-planned randomization generation number, and 2a, 2b in the phase 2a study to determine the difference between placebo and vaccine randomization is performed 1:2 in groups.

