4.1 Interim Analysis

Interim analyses were performed in stages.

- **Stage 1:** An assessment of AE's was performed after study Visit 1 for Group 1a.
- **Stage 2:** When all Phase I subjects (Groups 1a, 1b and 1c) had completed Visit 4, an interim analysis was performed to evaluate safety and antibody response.
In order for the study to move into Phase IIa study, the seroconversion rate for the binding antibody responses must be >70%. In addition, the incidence of Serious Adverse Events (Grade 3 or higher) related to the investigational product should be no more than 1 case.
- **Stage 3:** An interim analysis of Phase IIa study was performed after all patients complete their Visit 4. The purpose of this interim analysis was to provide options to placebo vaccinated subjects and to assess the safety of the vaccine after the second dose. For the interim analysis of Phase IIa, database locking was implemented before unblinding.

The study is unblinded at the post-vaccination visit (study Visit 4) at which time subjects are informed of their treatment assignment. Subjects who were assigned to the placebo group are offered to be vaccinated with GLS-5310. Subjects assigned to the placebo group who choose to be vaccinated with GLS-5310 are followed for a year from 1st GLS-5310 vaccination; subjects assigned to the placebo group but who decline vaccination with GLS-

CONFIDENTIAL

5310 are followed for a year from study entry as per the original study protocol.

5. Determination of Sample Size

This is an exploratory and descriptive Phase I/Ila clinical trial to evaluate the safety and immunogenicity of GLS-5310 for the purpose of preventing COVID-19, and dose not test statistical hypotheses, so the sample size is set within the limit of satisfying the research purpose. In the Phase I clinical trial, 45 subjects who meet the inclusion and exclusion criteria are registered to secure 15 subjects based on the allocation of each vaccination group. In the Phase Ila clinical trial, it is planned to secure 120 subjects based on randomization.

Randomization is performed 1:1 in 1b and 1c groups of Phase I clinical trial according to the planned random number, and 1:2 in placebo and vaccination groups in Phase Ila clinical trial to determine the difference between placebo and vaccination groups.

6. Analysis Sets

Safety and tolerability analyses will be performed on Safety Set.

✓ **Intention to treat (ITT)**

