10.2.1 Summary of Adverse Events

The following types of all AEs will be summarized with the number of subjects, incidence (%), 95% Clopper-Pearson's confidence interval and the number of events. In Phase IIa analysis, the differences in proportion between the groups will also be calculated with exact 95% confidence interval (Chan and Zhang 1999).

CONFIDENTIAL

The Solicited local AEs and Solicited Systemic AEs will be summarized for all TEAEs, all ADRs, all SAEs and all SADRs.

- TEAEs
- ADRs
- SAEs
- SADRs
- TEAEs leading to vaccination discontinuation
- Adverse Events of Special Interest

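### The Phase IIa power statements are for 300 and 126 participants, but the trial randomises 120 (80:40), and the figures for 300 do not carry over

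*Protocol*

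**What the plan says.** The Phase IIa part of the synopsis paragraph on sample size begins with "For the Phase IIa study, the sample size of 300 participants, randomized 2:1 vaccine to placebo". For that number it claims 82% power to detect an 18-point AE difference, and more than 95% power for a seroconversion difference of at least 10 points, both at alpha 0.05. It goes on to 126 participants, also 2:1, with 80% power for 28 AE points, and then: "A sample size of N=126 will allow detection of a difference in seroconversion of 14% with 80% statistical power". It names neither a test nor any placebo rate.

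Everywhere else Phase IIa has 120 participants. The synopsis header gives 120 and Table S1 lists 40 placebo and 80 vaccine. Protocol 11.6 says "it was planned to secure 120 subjects based on randomization", and SAP section 5 says "it is planned to secure 120 subjects based on randomization". None of these attaches a power, a detectable difference or a precision to 120, and nothing explains how 300 or 126 relates to it.

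The documents also differ on whether the trial is powered at all. The synopsis text on immunogenicity analysis says that it is powered to assess induction of immune responses. SAP section 5 says that it "dose not test statistical hypotheses, so the sample size is set within the limit of satisfying the research purpose". For AEs, SAP 10.2.1 plans estimation only: "the differences in proportion between the groups will also be calculated with exact 95% confidence interval".

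**The concern.** The two sentences on 300 participants stand in the current protocol as a description of what Phase IIa can detect, yet the trial enrols 40% of that number (120/300). A reader who takes them at face value would expect a real 18-point AE excess to be found about four times in five. Safety is a primary objective, so an unremarkable AE comparison could be read as more reassuring than 80 against 40 participants can support. No Phase IIa success rule depends on these tests, so what is at stake is the interpretation of the results, not a decision threshold.

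**Working it through.** **Inputs.** Differences, powers and totals come from the synopsis. The 2:1 allocation gives 200:100, 84:42 and 80:40 (Table S1 confirms 80 and 40). Two-sided 5% is from SAP 7.2, and Fisher's exact test for responder rates is from SAP 11.1–11.3. Placebo rates are not in the documents and are assumed over a range.

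**Formulas.** Let p0 be the placebo rate, p1 = p0 + d, and n1:n0 vaccine to placebo.
- Exact power = Σx Σy Bin(x; n1, p1) · Bin(y; n0, p0) · 1[Fisher two-sided p ≤ 0.05].
- Approximate placebo group size with r = 2: n0 = [1.96·√((r+1)·p̄·(1−p̄)) + zβ·√(r·p0(1−p0) + p1(1−p1))]² / (r·d²), where p̄ = (p0 + r·p1)/(r+1). The total is 3·n0.

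**Step 1: reproduce the plan's figures.**
- 14 seroconversion points, 80% (zβ = 0.8416), p0 = 0: p̄ = 0.0933, so n0 = (1.96·0.5039 + 0.8416·0.3470)²/0.0392 = 1.637/0.0392 = 41.8. Rounded up to 42, the total is **126**, as stated.
- 28 AE points, 80%, p0 = 30%: n0 = (1.96·0.8657 + 0.8416·0.8146)²/0.1568 = 36.2. With the continuity correction, n0·[1 + √(1 + 6/(2·n0·d))]²/4 = 41.4. Rounded up to 42, the total is **126**, as stated.
- 18 AE points, 82%: the continuity-corrected total is 297 at p0 = 30% and 309 at 36–40%. Fisher power at 200:100 is 83–84% for p0 = 35–50%. The stated 82% is reproduced closely.
- 10 seroconversion points: Fisher power at 200:100 is 99.9% at p0 = 0 and 96% at 1%, consistent with the claim of more than 95%. At 2% it is 90%.

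So the stated figures are not miscalculated for their own totals. The two results for 126 come out with and without a continuity correction respectively, which is a further reason to name the test.

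**Step 2: the same differences at the planned 80:40 (exact Fisher).**

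| Difference | Assumed placebo rate | N in text: power | 80:40: power |
|---|---|---|---|
| AE, 18 points | 35–50% | 300: 83–84% | 40–44% |
| Seroconversion, 10 points | 0–1% | 300: 96–99.9% | 38–41% |
| AE, 28 points | 20–50% | 126: 82–87% | 79–86% |
| Seroconversion, 14 points | 0% | 126: 85% | 80% |
| Seroconversion, 14 points | 2% | 126: 67% | 63% |
| Seroconversion, 14 points | 5% | 126: 55% | 51% |

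Uncorrected chi-square gives 49–55% for the 10-point row at 80:40.

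**Step 3: could another placebo rate rescue the claims for 300?** For 18 AE points, 80:40 gives 51% at a placebo rate of 20%, 73% at 5% and 84% at 2%. At those rates 200:100 would give 89%, 99% and 99.9%, so they are not the rates behind the stated 82%. For 10 seroconversion points, the highest Fisher power at 80:40 over all placebo rates from 0 to 90% is 78%, so 95% is never reached.

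**Step 4: what 80:40 does deliver.**
- The smallest differences above which Fisher power stays at or above 80% are 25.7–28.3 points for AEs (placebo 20–50%). For seroconversion they are 14.0, 17.2 and 19.7 points (placebo 0%, 2%, 5%).
- The expected 95% half-width for an AE difference (Wald) is 1.96·√(p1(1−p1)/80 + p0(1−p0)/40). With both rates 20%: 1.96·√(0.002 + 0.004) = 0.152. With both 50%: 1.96·√(0.003125 + 0.00625) = 0.190. These are the extremes for placebo 20–50% and true differences of 0–18 points. At 200:100 the range is 0.096–0.120.
- A seroconversion contrast of 70% against 0–5% has essentially 100% power.

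**The case against.** The strongest reply is that the same paragraph also gives figures for 126, only 5% above 120, so a reader who knows the planned number is shown nearly the right sensitivity. That largely stands. Moving from 126 to 120 costs about 4 points of power for the 14-point seroconversion difference and about 1–3 points for the 28-point AE difference. What remains is that the figures for 300 come first, are worded as the Phase IIa sample size, and are not marked as superseded. The 14-point figure also needs a placebo rate near zero that is nowhere stated. Reading 126 as 120 plus a dropout allowance would be a guess.

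A second reply is that power hardly matters in a descriptive trial. SAP section 5 supports this, but the protocol says that the study is powered for immune responses, and SAP 11.1–11.3 plan Fisher tests between arms. A descriptive rationale is also a reason to remove outdated power claims, not to keep them.

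It is also fair that nothing is miscalculated for its own total, and that the practical effect is limited: the numerical entry criterion of more than 70% seroconversion governs the move from Phase I to Phase IIa. This bounds the weight of the point but does not remove the mismatch.

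**Conclusion.** The point holds. The Phase IIa sensitivity in the synopsis belongs to a trial of 300 or 126, and nothing is stated for the 120 actually planned. Under placebo rates that reproduce the claims for 300, power at 80:40 is roughly half or less of what is stated: 40–44% against 82% for 18 AE points, and 38–41% against more than 95% for 10 seroconversion points. The figures for 126 carry over almost unchanged.

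The mismatch in numbers is plain from the text. The sizes rest on assumed placebo rates, two-sided 0.05, Fisher's test and all 80:40 being evaluable. The half-widths are Wald approximations; the exact interval planned in the SAP was not computed. This should be fixed as an error in how sensitivity is described. It is not evidence that the design fails.

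**What to change.** In the synopsis, delete the two sentences on 300 participants. Restate the sentences on 126 for 80 vaccine and 40 placebo, two-sided alpha 0.05, naming Fisher's exact test and the assumed placebo rates:
- AEs: 80% power for differences of about 26–28 points (placebo 20–50%). Since only intervals are planned, an expected 95% half-width of about 15–19 points may be given instead.
- Seroconversion: 80% power for differences of about 14, 17 or 20 points (placebo 0%, 2%, 5%). Add that these assume every sample is evaluable, because missing immunology results are not imputed.

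Present these figures as the sensitivity of a descriptive trial, so that the paragraph agrees with SAP section 5. The tests in SAP 11.1–11.3 can stay as planned.

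The cost is protocol wording only: no added participants and no changed analysis. The stated sensitivity becomes less favourable.

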VAS Score	X		X		X	X				
Collect blood for serum ⁸	X		X		X	X	X	X	X	
Collect blood for PBMCs ⁹	X		X		X	X	X	X	X	
Estimated blood volume										
Maximum blood volume collected	60	10	50		60	50	50	50	60	

* If there are test results for safety evaluation items within 1 week from the first investigational product vaccination date, it can be used

Check the occurrence of adverse events by telephone.

1 Written Informed Consent must be obtained PRIOR to any study procedures; document that a completed copy has been provided to participant.

2 At enrollment, a full physical exam is performed; height and weight are recorded. At follow-up and unscheduled visits, only a targeted physical exam is performed determined by the presence of symptoms and directed to those organ systems only.

3 Blood for Hematology: RBC, hemoglobin, hematocrit, platelet, WBC, neutrophil, lymphocyte, monocyte, eosinophil, basophil

4 Blood for Chemistry Testing: Sodium, potassium, glucose, BUN, Cr, ALT, Bili, Ca, Cl, AST, ALP, CPK, albumin, total protein, total cholesterol

5 Serological test: Hepatitis B (HBsAg), Hepatitis A (IgG and IgM), HIV, Hepatitis C- HCV RNA testing, if necessary

6 Obtain HgbA1c if test result within past 3 months is not available

7 Subject diary their responses up to 7 days after vaccination of the investigational product on the clinical trial-related record sheet distributed to the investigator. Diaries are collected and reviewed at indicated visits

8 For serum, collect 1 x 10 mL red top or serum separator tubes;

9 For PBMCs, collect 4 x 10 mL ACD tubes;

Table S3: Schedule of Events (Vaccinations at 0 and 12 weeks, Phase 1 study ONLY)

Tests and Observations	Visit 1	Visit 2	Visit 3	Tele phone Visit 1 [#]	Visit 4	Visit 5	Visit 6	Visit 7	Visit 8	Unscheduled
Time relative to enrollment	Screen, Enroll	Week 1	Week 12	Week 13	Week 16	Week 20	Week 24	Week 36	Week 48	N/A
Permitted window (days)		±2d	±3d	±3d	±3d	±4d	±7d	±7d	±7d	N/A
Clinical Evaluations										
Obtain Informed Consent ¹	X									
Review Eligibility Criteria	X									
Review and Record Medical History	X									
Review and Record Demographics	X									
Review Record Prior and Concomitant Meds	X	X	X		X	X	X	X	X	X
Physical Exam and Vital Signs ²	X	X	X		X	X	X	X	X	X
Safety Evaluations										
Record Adverse Events	X	X	X	X	X	X	X	X	X	X
Examine injection site and record findings	X	X	X	X	X					X
Blood for Hematology ³ : CBC with differential	X	X			X					X

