Blood for Chemistry Testing ⁴ : Sodium, potassium, glucose, BUN, Cr, ALT, Bili	X	X			X					X
Serological test ⁵	X									
Chest X-ray	X									
12-lead ECG	X									
PCR or Antibody test for SARS-CoV-2	X									
Urine for pregnancy testing (as applicable)	X		X							
Study Related Procedures										
Administer vaccine	X		X							
Subject Diary ⁶	X	X ⁷	X		X ⁷					
VAS Score	X		X							
Collect blood for serum ⁸	X		X		X	X	X	X	X	
Collect blood for PBMCs ⁹	X		X		X	X	X	X	X	
Estimated blood volume										
Maximum blood volume collected	80	10	70		80	70	70	70	80	

Check the occurrence of adverse events by telephone.

1 Written Informed Consent must be obtained PRIOR to any study procedures; document that a completed copy has been provided to participant.

2 At enrollment, a full physical exam is performed; height and weight are recorded. At follow-up and unscheduled visits, only a targeted physical exam is performed determined by the presence of symptoms and directed to those organ systems only.

3 Blood for Hematology: RBC, hemoglobin, hematocrit, platelet, WBC, neutrophil, lymphocyte, monocyte, eosinophil, basophil

4 Blood for Chemistry Testing: Sodium, potassium, glucose, BUN, Cr, ALT, Bili, Ca, Cl, AST, ALP, CPK, albumin, total protein, total cholesterol

5 Serological test: Hepatitis B, Hepatitis A, HIV, Hepatitis C

6 Subject diary their responses up to 7 days after vaccination of the investigational product on the clinical trial-related record sheet distributed to the investigator.

7 The investigator collects and reviews the records related to the clinical trial.

8 For serum, collect 1 x 10 mL red top or serum separator tubes;

9 For PBMCs, collect 4 x 10 mL ACD tubes;

Table S4: Schedule of Events (Phase IIa subjects assigned to the placebo group who choose to be vaccinated with GLS-5310 at study visit #4: Vaccinations at 0 and 8 weeks)

Tests and Observations	Visit 1	Visit 2	Visit 3	Tele Visit	Visit 4	Visit 5	Visit 6	Visit 7	Visit 8	Un-sched
Time relative to enrollment	Screen Enroll	Wk 1	Wk 8	Wk 9	Wk 12	Wk 20	Wk 24	Wk 36	Wk 48	N/A
Permitted window (days)		±2d	±3d	±3d	±3d	±4d	±7d	±7d	±7d	N/A
Clinical Evaluations										
Obtain Informed Consent ¹	X									
Review Record Prior and Concomitant Meds	X	X	X		X	X	X	X	X	X
Physical Exam and Vital Signs ²	X	X	X		X	X	X	X	X	X
Safety Evaluations*										
Record Adverse Events	X	X	X	X	X	X	X	X	X	X
Examine injection site and record findings	X	X	X	X	X					X

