3. STUDY DESIGN

This Phase I / II study will assess the safety, tolerability, and immunogenicity of GLS-5310 DNA vaccine.

The Phase I study is an open-label, dose escalation study to assess two dose levels of GLS-5310 DNA vaccine (0.6 and 1.2 mg) and given via two vaccination regimen (0-8 weeks and 0-12 weeks). Participants will be randomized to one of the three treatment arms. GLS-5310 will be administered via intradermal (ID) injection using the Mantoux technique followed by suction applied over the vaccination site using the JM-11 device. The primary outcome measures are the safety and tolerability of GLS-5310 given ID with JM-11 and binding antibody responses elicited by vaccination. Secondary outcome measures are the T cell responses elicited to vaccine antigens and neutralizing antibody titers.

Dose escalation within the Phase I portion of the study will occur as follows. Study arm 1a (0.6 mg per vaccination) will be vaccinated and followed to the Week 1 safety visit. If no vaccine-associated severe adverse events (SAEs) have been documented, then enrollment into study arms 1b and 1c (1.2 mg per vaccination) will occur in a randomized manner. An interim analysis will occur after visit 4, four weeks after the 2nd vaccination to assess safety and binding antibody responses. Escalation to Phase II will occur based on this analysis. The choice of regimen for the Phase II study will be determined after review of study objectives.

The Phase IIa study is designed as a randomized, double-blind, placebo-controlled study with only a single active study drug arm. Subjects will be randomized to receive either placebo or GLS-5310 vaccine in a 1:2 ratio. The primary and secondary goals of the Phase II study are the same as the Phase I study. An interim analysis will be performed at Visit 4, one month after the final vaccination. The study will be unblinded at the post-vaccination visit (study visit 4) at which time subjects will be informed of their treatment assignment. Subjects who were assigned to the placebo group will be offered to be vaccinated with GLS-5310. Subjects assigned to the placebo group who choose to be vaccinated with GLS-5310 will be followed for a year from 1st GLS-5310 vaccination (Table S4); subjects assigned to the placebo group but who decline vaccination with GLS-5310 will be followed for a year from study entry as per the original study protocol.

[Sub-studies]

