5.2 Administration of GLS-5310 vaccine

ID vaccine administration with JM-11 is performed by first administering vaccine (0.1 mL) intradermally via Mantoux injection with a 1 mL tuberculin syringe with a 25 or 26 gauge needle (Figure 5.2-A) that generates a bleb or “bubble” in the skin. It is important that the needle angle be very shallow as shown in the photo. After injection, a clean tip is applied on the JM-11 device, the opening of the tip of the JM-11 device (Figure 5.2-1b) is applied over the bleb, encircling as much of the bleb as possible. The JM-11 device is then turned ON by pressing the button and held in place while suction is applied. The JM-11 device will turn off automatically after 30 seconds. After use, the tip is discarded, the device cleaned with an alcohol wipe, and then placed into a plastic bag and labelled with the participant’s name. For this study, devices will *NOT* be shared between participants.

Figure 5.2-1 A) Example of ID Mantoux injection and B) JM-11 device.

Following vaccine administration, the participant will be asked to assign a VAS score for the administration event itself and again at 15-20 min.

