8.1.5 Safety Laboratory Evaluations

Blood for a complete blood count with differential(RBC, hemoglobin, hematocrit, platelet, WBC, neutrophil, lymphocyte, monocyte, eosinophil, basophil) and chemistries (consisting of sodium, potassium, blood urea nitrogen (BUN), creatinine, glucose, ALT, and bilirubin, Ca, Cl, AST, ALP, CPK, albumin, total protein, total cholesterol) will be performed at Visits 1, 2, 4 and 8. A urine pregnancy test will be performed at Visit 1 and Visit 3 for those of childbearing potential. Laboratory test abnormalities are generally not recorded as adverse events or serious adverse

events. According to the judgment of the investigator, a clinically significant abnormal value is reported as an adverse event, and if it is related to a clinical adverse event, it is reported as the name of the adverse event. For laboratory test results, normal/abnormal evaluation is performed according to the normal range of the clinical trial site, and the severity is evaluated by the Toxicity Grading Scale.

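### Table S3's blood-volume row and its Week 48 laboratory marks contradict its own footnotes and the protocol text

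*Protocol*

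**What the plan says.** Table S1 of the protocol synopsis puts arm 1b (1.2 mg, weeks 0 and 8) on Table S2 and arm 1c (1.2 mg, weeks 0 and 12) on Table S3, with 15 participants each. Both Phase IIa arms are on S2.

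- **Tubes.** Footnotes 8 and 9 read the same in S2, S3 and S4: "For serum, collect 1 x 10 mL red top or serum separator tubes" and "For PBMCs, collect 4 x 10 mL ACD tubes".
- **Maximum blood volume, Visits 1 to 8.** S2 and S4 print 60, 10, 50, 60, 50, 50, 50, 60. S3 prints 80, 10, 70, 80, 70, 70, 70, 80.
- **Safety laboratory tests.** Section 8.1.5 says haematology and chemistry "will be performed at Visits 1, 2, 4 and 8", with no distinction by arm. Section 7.1.10 lists them at Visit 8, and Section 7.1.11 lists none at unscheduled visits. S2 marks Visits 1, 2, 4 and 8. S3 marks Visits 1, 2, 4 and Unscheduled.
- **Scope of S3.** Its heading is "Table S3: Schedule of Events (Vaccinations at 0 and 12 weeks, Phase 1 study ONLY". The synopsis paragraph on Phase IIa nevertheless cites Table S3 for the follow-up of placebo participants who decline GLS-5310. The matching paragraph of Section 3 cites no table for them.
- **VAS.** Section 5.2 says that after vaccine administration the participant is "asked to assign a VAS score for the administration event itself and again at 15-20 min". S2 and S4 mark VAS at Visits 1, 3, 4 and 5; S3 marks Visits 1 and 3.
- **HgbA1c.** Section 7.1.1, whose parent heading covers S2 and S3, lists it for diabetics at Visit 1. S2 has a row and a footnote for it; S3 has neither.

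**The concern.** Sites work from schedule tables. For arm 1c they hold two incompatible statements of how much blood is drawn, a figure that bears on participant burden and safety. They also hold a table that, as printed, omits the end-of-study safety laboratory tests which the text requires of every arm.

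SAP 10.4 summarises laboratory values and change from baseline at each timepoint by group. If the printed marks were followed, arm 1c would have no scheduled entry at Visit 8. SAP 10.3 treats VAS the same way, so Visits 4 and 5 would be filled for arm 1b and empty for arm 1c.

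The reference for placebo decliners could carry the same problem into Phase IIa. It also fits poorly: Week 12 is the second vaccination visit in S3, whereas these participants had their injections at weeks 0 and 8 and reach Visit 4 at Week 12.

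**Working it through.** **Inputs**
- Serum 1 × 10 = 10 mL and PBMC 4 × 10 = 40 mL (footnotes 8 and 9).
- Immunology draws at every scheduled clinic visit except Visit 2 (Section 7.5): Visits 1 and 3 to 8.
- Laboratory draw 10 mL. This is inferred from Visit 2, which has laboratory tests but no serum or PBMC draw and shows 10 in every table.
- The volume rows print no unit; mL is assumed from the footnotes.

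**Formula.** Volume at a visit = I × (10 + 40) + L × 10, where I and L are 1 if the visit has an immunology draw or a laboratory draw, and 0 otherwise.

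**Reproducing S2 first.** With laboratory tests at Visits 1, 2, 4 and 8, the formula gives 60 + 10 + 50 + 60 + 50 + 50 + 50 + 60 = 390. Every entry matches the printed row.

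**S3 with the same tubes**

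| | V1 | V2 | V3 | V4 | V5 | V6 | V7 | V8 | Total |
|---|---|---|---|---|---|---|---|---|---|
| Printed in S3 | 80 | 10 | 70 | 80 | 70 | 70 | 70 | 80 | 530 |
| Footnotes, laboratory tests as in 8.1.5 | 60 | 10 | 50 | 60 | 50 | 50 | 50 | 60 | 390 |
| Gap | 20 | 0 | 20 | 20 | 20 | 20 | 20 | 20 | 140 |

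The gap is 7 × 20 = 140 mL, and 140/390 = 36%.

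**Other laboratory schedules do not close it**
- Laboratory tests only where S3 marks them (none at Visit 8): Visit 8 becomes 50 mL, the total 380 mL and the Visit 8 gap 30 mL.
- Laboratory tests also at Visit 3, which Section 7.1.3 lists but neither the tables nor 8.1.5 do: Visit 3 becomes 60 mL, the total 400 mL and the Visit 3 gap 10 mL.

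**What S3's row would need.** Visits 3, 5, 6 and 7 have no laboratory draw under 8.1.5 and show 70, so serum plus PBMC would have to be 70 mL and not 50. Then 70 + 10 = 80 at Visits 1, 4 and 8, and 10 at Visit 2, which fits the whole row. The row therefore needs tubes that the footnotes do not list, and a laboratory draw at Visit 8 that the S3 marks do not show.

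**Laboratory marks side by side**

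| Source | Visit 8 | Unscheduled |
|---|---|---|
| S2 rows | yes | no |
| Section 8.1.5 | yes | not listed |
| Sections 7.1.10 and 7.1.11 | yes | no |
| S3 volume row | implied (70 at Visits 5–7, 80 at Visit 8) | no figure |
| S3 haematology and chemistry rows | no | yes |

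**VAS.** Section 5.2 ties the score to the injection. Sections 7.1.1 and 7.1.3 list it at the two vaccination visits; 7.1.5 and 7.1.6 list none at Visits 4 to 7. The Visit 4 and 5 marks in S2 and S4 have no counterpart in the text.

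**What agrees between 1b and 1c.** Adverse events are recorded at every visit in both tables. Serum and PBMCs are taken at Visits 1 and 3 to 8 with the same footnoted tubes. Visit 4 falls four weeks after the second dose in both (12 − 8 = 4; 16 − 12 = 4).

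**The case against.** Three replies deserve weight.

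First, the volume row is labelled as an estimate and a maximum, so 70 and 80 mL might be ceilings, and 36% would then compare printed limits and not planned draws. That is possible but strained: S2 and S4 use the same labels for exact sums, and S3 allows no margin at Visit 2.

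Second, the laboratory point depends on which of two adjacent columns holds a mark, and column positions in text taken from a PDF can shift. S2, for example, keeps its consent footnote but shows no consent row. Against this, both S3 laboratory rows show the same placement, while the S3 serum and PBMC rows end correctly at Visit 8. A shift cannot be excluded, and the page itself should be checked.

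Third, Sections 7.1 and 8.1.5 already give both arms one laboratory procedure. That limits the likely harm, because a site following the text would draw at Visit 8. It does not remove the contradiction for a site following the table.

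**Conclusion.** S3 contradicts its own footnotes on blood volume (530 against 390 mL), and as printed it contradicts Sections 8.1.5, 7.1.10 and 7.1.11 on Week 48 laboratory tests. The volume finding is firm, given mL as the unit and 10 mL per laboratory draw. The laboratory finding is conditional on the column position being as it appears; if so, all 15 arm 1c participants are affected under S3. Phase IIa decliners would be affected too if the synopsis reference is taken literally; their number is not given. The VAS and HgbA1c mismatches are minor. The documents do not say which volume, or which entry of each conflicting pair, is intended.

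A reader might infer more, and the documents do not support it:

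- **That the 1b and 1c contrast is not measured alike.** Section 3.1 bases the regimen choice on adverse events and binding antibody after Visit 4, and those are collected alike. Table S1 already sets Phase IIa at weeks 0 and 8, and SAP 11.1 says Part 1 is not powered to separate regimens. Nor is it undisputed that this is the only randomised Phase I contrast. Section 11.6 says "Randomization was performed 1:1 in groups 1b and 1c of the phase 1 study", while Section 3 says "Participants will be randomized to one of the three treatment arms", although Section 3's next paragraph randomises only 1b and 1c.
- **That the arms had different eligibility checks.** Exclusion criterion 18 applies the hepatitis, HIV and HCV RNA provisions to everyone, and Section 7.1.1 lists HgbA1c for both schedules.
- **That arm 1c had about 50% more cells for ELISpot.** This assumes that the extra 20 mL is all PBMC (60 against 40 mL), against footnote 9. Results are in any case expressed per million cells.

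**What to change.** Reconcile the following, with the sponsor stating which entry is intended in each pair:

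1. S3's volume row with its footnotes 8 and 9, so that the row adds up from the listed tubes.
2. S3's haematology and chemistry marks with Sections 8.1.5, 7.1.10 and 7.1.11. Settle the Visit 3 laboratory entry in Section 7.1.3 at the same time.
3. The synopsis reference sending Phase IIa placebo decliners to S3 with S3's heading and with Table S1.
4. The VAS marks at Visits 4 and 5 in S2 and S4 with Sections 5.2, 7.1.5 and 7.1.6.
5. The missing HgbA1c row in S3 with Section 7.1.1.

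SAP 4.1 reports the Phase I Visit 4 analysis as done, so arm 1c may already have been run on S3. If it was run on S3 as printed, the SAP or study report should state which schedule was followed and flag the Week 48 laboratory and Visit 4–5 VAS summaries as not comparable between 1b and 1c.

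The cost is table wording and, if needed, one reporting note.
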